If these conditions are not met on Day 15 or Day 29 (all +/- 3 days), the subject will be evaluated weekly and Panax ginseng will not be initiated until the toxicity has resolved as described above. The patient can be off the drug for a total 1 week before being removed from the treatment phase of the study.

January 21, 2016 Page 15 of 33 INSTRUCTIONS FOR DOSE MODIFICATIONS OR INTERRUPTION DURING A TREATMENT PHASE.

NCI CTC 4 Toxicity Grade	Day 2- 57
Grade≥ 2 neutropenia related to Panax ginseng or placebo associated with fever (temperature ≥ 38.5° C) or Grade 4 neutropenia	 Discontinue Panax ginseng study drug or identical placebo.
Thrombocytopenia Panax ginseng or placebo ≥Grade 2 (platelet count < 50,000/mm³)	 Discontinue Panax ginseng study drug or identical placebo
Steven Johnson syndrome	 Discontinue Panax ginseng study drug or identical placebo
Desquamating (blistering) rash- any Grade	 Discontinue Panax ginseng study drug or identical placebo.
Rash, Erythema multiforme ≥ ≥Grade 2	 Discontinue Panax ginseng study drug or identical placebo.
Hypertension, Hypotension, cardiac arrhythmia ≥Grade 2	 Hold (interrupt) dose, Up to one week before taking off study Follow at least weekly. If the toxicity resolves to ≤ grade 1 restart dose at (400mg) level and continue the study medication with continued monitoring as prescribed in the protocol. If the patient has repeat cardiac arrhythmias ≥ Grade 2. He will be discontinued from the study medication and monitored.
≥ Grade 3	Discontinue Panax ginseng study drug or identical placebo.
Allergic reaction or hypersensitivity ≥Grade 2	 Hold (interrupt) dose, Up to one week before taking off study Follow at least weekly. If the toxicity resolves to ≤ grade 1 restart dose at (400mg) level and continue the study medication with continued monitoring as prescribed in the protocol. If the patient has repeat ≥ Grade 2 allergic or hypersensitivity reaction, he will be discontinued from the study medication and monitored.
>/= Grade 4	 Discontinue Panax ginseng study drug or identical placebo
	placebo.

NCI CTC 4 Toxicity Grade	Day 2- 57

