Any Other non- hematologic toxicity assessed as Panax ginseng study drug or identical placebo - related ≥ Grade 2 including insomnia, anxiety, restlessness, behavioral change, dizziness, vertigo, tachycardia, diahhrea, nausea/vomitting, headache, increased menstrual bleeding and breast tenderness	 Hold (interrupt) dose. Follow at least weekly. If the toxicity resolves to ≤ grade 1 restart dose at (400mg) level and continue the study medication with continued monitoring as prescribed in the protocol. If the patient has repeat ≥ Grade 2 non-hematological toxicity, they will be discontinued from the study medication and monitored.

III. Discontinuation of Study Treatment

Treatment will continue until Day 29±3 and Day 57±3 for participants eligible for the open label phase.

Treatment with study drug is to be discontinued when any of the following occurs:

- Adverse event(s) that, in the judgment of the Investigator, may cause severe or permanent harm or which rule out continuation of study drug.
- Major violation of the study protocol.
- Withdrawal of consent
- Lost to follow up
- Death
- Suspected pregnancy

Major violation will be determined by the PI. Major violation will include lack of consent, lack of safety laboratory tests. These will be reported to IRB and FDA in a timely fashion.

Figure 6. Study Design

Phase I(1st 30 patients)

Table 3. Study Assessments

ASSESSMENTS	Baseline	Day 8 (± 3)Ph#	Day 15 (± 3)	Day 21 (± 3)Ph#	Day 29 (± 3)	Day 36 (± 3) Ph#	Day 43 (± 3)Ph#	Day 57 (± 3)
Medical History	Х							
Physical Examination	X							
Zubrod Score	Х							
Medication Review	Х	Х	Х	Х	Х	Х	Х	Х
Symptom and QoL Assessment								
ESAS	Х	Х	Х	X	Х	Х	Х	Х
HADS	Х		Х		Х			Х
FACT-G &FACIT-F subscale	X		×		X			X
SDMT	х		х		х			х
GSE**					x			х
Physical Activity								
6 minute walk test	X		X		X			X
Hand grip Strength and Endurance test	X		X		X			X
Hematology/ Chemistry*	X		X		X			X
Pregnancy Test [@]	Х							
Optional Blood	x		x		x			
Draws Toxicity Evaluation	X	X	X	X	X	X	X	X

* CBC, Electrolytes, Total bilirubin, and AST (SGOT) and ALT (SGPT will be done at Baseline, CBC and Electrolytes will be done at Day 15+/-3days and Day 29+/- 3days. We would monitor the PT/INR weekly for patients on coumadin and liver function test every 2 weeks (Total bilirubin, and AST (SGOT) and ALT (SGPT) if hepatic metastases are present or if patients are on potentially hepatoxic agents such as acetaminophen or statins.

**GSE - Global symptom evaluation

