#Assessment via telephone or in person

@ Pregnancy test to be performed no greater than 14 days prior to consent in study.

If patients are unable return to the clinic for any of the scheduled assessment days (Day 15, Day 29, Day 36, and/or Day 57), we will contact the patient via telephone to complete the symptom and quality of life assessments (ESAS, HADS, FACT-G, FACIT-F, and GSE). If contacted by phone, then physical assessments will not be performed.

Adverse events will be captured according to the recommended AE recording guidelines for a Phase II protocol.

C.7. Symptom Assessment

C.7.1. Demographic variables

Demographic variables will include patient self-reported birth date, sex, marital status, ethnicity, education, and job status, primary cancer, cancer treatment within the last year, surgery, chemotherapy, immunotherapy or radiotherapy, and medications including opioid dosage. **(APPENDIX P).** Appendix P also includes tracking the baseline labs ordered and an off study note that will be completed once the patient has been taken off study.

C.7.2.Symptom assessment (see Table 3)

The Functional Assessment of Chronic Illness Therapy-Fatigue (FACIT-F) (including the Functional Assessment of Chronic Illness-General (FACT-G) and Fatigue subscales), Hospital Anxiety and Depression Inventory (HADS), Edmonton Symptom Assessment System (ESAS), Symptom Digit Modalities Test (SDMT) and Six minute walk test, will be used assess outcomes.

Adherence: Patients with similar characteristics to those of patients we will admit to the study have demonstrated strong adherence to assessments of the same duration in studies conducted by our group [128,129,137,138]. These assessment tools have been validated and are reliable for use in the collection and analysis of data. Also patients in this study with not undertake time intensive radiological tests such as MRI'S or drug pharmacokinetic studies which are a common part of clinical trials. This would enable help in completion and minimize attrition.

C.7.2.1. Outcome Measures

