This is a preliminary study to explore the efficacy of P. ginseng in reducing fatigue as measured by the Functional Assessment of Cancer Therapy- Fatigue (FACIT-F) subscale. Because this Panax ginseng has not been previously evaluated in cancer related fatigue, we will implement this study in two phases. In the first phase(initial non dose escalating phase), we will enroll up to 30 patients in the Arm 2 (treatment arm); patients will not be enrolled in the placebo arm. Recruitment will be halted until these original 30 patients can be evaluated for DLTs. In the second, main phase patients will be randomized to receive either Panax ginseng or placebo. As a

2009-0854 January 21, 2016 Page 23 of 33

primary analysis, we will assess the level of fatigue at baseline and after 29 days to determine group differences in fatigue changes over time using analysis of variance. This analysis will test for differences between groups, differences over time, and a group by time interaction. We will also perform a repeated measures analysis by group using all available time points (for the FACIT-F fatigue subscale at baseline, day 15 and day 29). This analysis will test for differences between groups, differences over time, a group by time interaction, and trends over time. For all analyses of continuous variables, if the data are not approximately normally distributed, we will either use a nonparametric equivalent of the statistical test or we will transform the variable to achieve approximate normality. The design of the study is intent to treat, i.e., it is our aim to analyze anyone who received at least a single dose for both toxicity and response. Response would be considered clinical beneficial if they improve 3.5 points on the FACIT- F fatigue subscale at day 29 or day 15 (if day 29 is unavailable). Patient who have not completed at least day 15 would be considered inevaluable for consideration of clinical benefit.

Pilot Analysis:

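### Two dose-hold rows end with the patient off study, the text above them ends only the treatment phase, and nothing secures the Day 29 FACIT-F for these patients in the primary analysis

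*Combined protocol and SAP*

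**What the plan says.** The rules on holding study drug stand under *Dose Continuation, Modification and Interruption* (within C.6.2).

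- **Text above the dose-modification table**, attached to the Day 15 and Day 29 start conditions: "The patient can be off the drug for a total 1 week before being removed from the treatment phase of the study".
- **Cardiovascular row and allergic-reaction row**, each for Grade 2 or higher: "Hold (interrupt) dose, Up to one week before taking off study".
- **Row for any other related non-hematologic toxicity**, Grade 2 or higher: "Hold (interrupt) dose. Follow at least weekly". It gives no limit and does not mention leaving the study.
- **Repeat arrhythmia**, in the cardiovascular row: "He will be discontinued from the study medication and monitored". Repeat events in the other two hold rows end in the same way.

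Elsewhere, C.6.2 uses being taken off the study for the end of participation on Day 57. C.7.1 provides for "an off study note that will be completed once the patient has been taken off study".

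On collection, the notes to Table 3 say "If patients are unable return to the clinic for any of the scheduled assessment days", then "we will contact the patient via telephone to complete the symptom and quality of life assessments"; FACIT-F is among the instruments listed.

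On analysis, C.9 describes the design as intent to treat: "it is our aim to analyze anyone who received at least a single dose for both toxicity and response". Under *Power Considerations*, the same section omits dropouts from the primary analysis and carries the last FACIT-F score forward only in a secondary one.

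**The concern.** A hold that outlasts its limit leads to two different statuses, depending on which line the site follows. One ends treatment. The other, taken at its word, ends participation. The difference matters because the primary endpoint is a questionnaire score at Day 29, which can be obtained whether or not the patient is still taking capsules.

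No section says that FACIT-F continues after study drug stops. The telephone provision is written for patients who cannot come to clinic, not for patients taken off study. A patient closed out before Day 29 therefore has no primary outcome and, as a dropout, is left out of the primary analysis. At stake is whether that analysis compares the arms as randomized or only those patients whose adverse events did not remove them.

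**Working it through.** **1. The wording side by side.** The table rows themselves distinguish stopping medication with monitoring (repeat events) from being taken off study (a hold over one week). C.6.2 and C.7.1 use off study as a participant status. The literal reading is therefore a reasonable one for a site, though not the only one.

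**2. Who can be affected.** Two of the three hold rows carry the wording. A hold that starts on Day 8 reaches one week on Day 15. A hold that starts after Day 22 cannot reach one week before Day 29 (22 + 7 = 29). The exposed group is patients with an unresolved cardiovascular or allergic event of Grade 2 or higher whose hold begins by about Day 22.

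**3. The plan's own figures reproduce.** Inputs from *Power Considerations*: SD of change 5.8, 50 evaluable per arm, two-sided 0.05, 80% power.

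- Detectable difference = (1.96 + 0.84) × 5.8 × √(2/50) = 3.25 by the normal approximation, or 3.28 by the t-test. The plan states 3.3.
- Power for 3.3 points with 50 per arm: 81.2% (normal) or 80.4% (t-test).
- Recruitment: 50/0.8 = 62.5, so 63 per arm. The plan states 64, which leaves 64 × 0.8 = 51.2 at 20% dropout.

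The sample size is not in question. Nor is power the main issue: six extra losses in one arm (45 against 51) leave about 79.4%.

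**4. Size of a possible bias.** Suppose a share *p* of an arm is removed, and the mean change of those removed is *g* points worse than that of those who stay. The full-arm mean is then (stayers' mean) − *p*×*g*, so the completers overstate the arm by *p*×*g*. With the same *g* in both arms, the bias in the arm difference is *q*×*g*, where *q* is the excess share removed in one arm. Both *q* and *g* are assumptions; the documents give neither. The error rates below apply under no true effect, with 51.2 analyzed per arm. The standard error is SD × √(2/51.2): 1.15 at SD 5.8 and 1.74 at the plan's alternative SD of 8.8.

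| q (assumed) | g (assumed) | Bias = q×g | Share of 3.3 | Two-sided error, SD 5.8 | Two-sided error, SD 8.8 |
|---|---|---|---|---|---|
| 2% | 5 | 0.1 | 3% | 0.051 | 0.050 |
| 10% | 5 | 0.5 | 15% | 0.072 | 0.060 |

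The sign follows the signs of *q* and *g*. If either is reversed, so is the bias.

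**5. Whether the analysis plan repairs the loss.** The Day 15 fallback in C.9 applies only to the exploratory clinical-benefit response. The repeated-measures analysis can use a Day 15 score but is additional to the primary analysis. Carrying the last score forward is secondary, and for a patient closed out before Day 15 the only score is baseline. None of these supplies a Day 29 value for the primary analysis.

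**The case against.** The strongest reply is that this is loose wording. Off study may simply mean off study drug. *III. Discontinuation of Study Treatment* deals only with treatment, Table 3 exempts nobody who has stopped drug, a telephone route exists, and C.6.2 follows patients for up to 30 days after the last dose. All of this stands against the stronger inference that the plan tells sites not to collect the score; no section does so. It does not remove the ambiguity: the 30-day follow-up names no questionnaire, and off study is used elsewhere as a participant status.

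A reader might also infer three conflicting endings. The third hold row is silent on a limit, which is not a third ending, and the sentence above the table may be meant to cover it.

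A reader might further infer that removal is triggered by study-drug toxicity and so favors ginseng. The documents do not support that. The two rows require no attribution to study drug, and they apply identically and under blinding in both arms. No toxicity rates by arm are given for this product. The comparative studies summarized in B.3.5 (American ginseng) and B.4.2 (Korean red ginseng) report no significant difference in adverse events. Nothing shows that patients with these events have worse fatigue change, and the introduction calls P. ginseng a stimulant, so the opposite is conceivable. That B.7 names hypertension and hypersensitivity as concerns to monitor makes a difference between arms possible, not established.

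Finally, large losses look unlikely. C.3.2.2 excludes Panax allergy, a history of arrhythmias and uncontrolled hypertension, and commoner effects such as insomnia, nausea and headache fall in the row without the off-study wording. That also stands, and it places the 10% figure toward the high end.

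**Conclusion.** The point holds as an inconsistency with a consequence for the primary endpoint. Two hold rows can be read to end participation before Day 29, the adjoining text ends only the treatment phase, and the primary analysis then omits the patient, contrary to the aim of analyzing everyone dosed. Bias arises only if removals differ by arm and the patients removed differ in fatigue change. Its direction and size cannot be determined from the documents.

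Under the assumed excess loss of 2% to 10% and gap of 5 points, the bias is 0.1 to 0.5 points, or 3% to 15% of the detectable difference. That is modest, and probably nearer the lower end given how few patients the two rows are likely to catch. The point still merits correction because a score that was not collected cannot be recovered at analysis, and the change costs very little.

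**What to change.** 1. Reconcile the two table rows, the row with no limit and the sentence above the table on what happens when a hold exceeds its limit. The length of the hold and the stopping rule are for the sponsor to decide.
2. Whichever wording is kept, state that patients who stop study drug still complete the Day 15 and Day 29 FACIT-F, by telephone if needed, unless they withdraw consent, are lost to follow-up or die. Extend the telephone note to Table 3 to cover these patients explicitly.
3. In C.9, state that these scores enter the primary analysis, and that a patient who stopped study drug but has a Day 29 FACIT-F is not a dropout. Without this, the scores could be collected and still be excluded.

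The cost is a wording change in a few places and one or two telephone questionnaires for a few patients.

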CBC, Electrolytes, Total bilirubin, and AST (SGOT) and ALT (SGPT will be done at Baseline, CBC and Electrolytes will be done at Day 15+/- 3days and Day 29+/- 3days. We would monitor the PT/INR weekly for patients on coumadin and liver function test every 2 weeks (Total bilirubin, and AST (SGOT) and ALT (SGPT) if hepatic metastases are present or if patients are on potentially hepatoxic agents such as acetaminophen or statins. Laboratory studies will be performed at baseline, day 15, and day 29. Hematology and chemistry blood collection will be performed on the expanded open label cohort of patients at Day 57 or conclusion of P. ginseng. Patient can have the labs drawn at outside facility. The research nurse will obtain results from outside labs via fax, or email. Patients entered on the open label phase will be followed until their respective study conclusion.

Day 15, 29, and 57 safety labs and Day 15 and 29 optional research blood will be collected only if patient returns to MDACC for the follow-up visits.

Dose Continuation, Modification and Interruption

II. Dose Continuation, Modification and Interruption

Subjects will be evaluated for AEs with the NCI CTCAE v4.0 as a guide for the grading of severity.

Table A outlines Panax ginseng/placebo dose reduction steps

Table A: Panax ginseng/ placebo Dose Reduction Steps				
Starting Dose	400mg capsule or identical placebo orally BID for 28 days			
Dose Level –1	400 mg daily or identical placebo for rest of the treatment phase (up to day 29)			

INSTRUCTION FOR INITIATION OF A WEEK 3, AND OPEN LABEL

Prior to initiation of treatment of day 15, and open label phase (Day 29) the patient should have:

We would monitor the PT/INR weekly for patients on coumadin and liver function test every 2 weeks[day 15 +/-3 days, and day 29+/-3 days (Total bilirubin </=1.5 mg/dL, and AST (SGOT) and ALT (SGPT) </=2 x ULN or </= 5 x ULN)if hepatic metastases are present or if patients are on potentially hepatoxic agents such as acetaminophen or statins.

- Any Panax ginseng-related or identical placebo related allergic reaction/hypersensitivity that may have occurred has resolved to ≤ grade 1 severity;
- Any other Panax ginseng-related or identical placebo -related adverse event that may have occurred has resolved to ≤ grade 2 severity.

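### By default the dose-modification table restarts study drug after a first Grade 3 allergic reaction that resolves; its first-event stop is Grade 4, while the cardiovascular row stops at Grade 3

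*Combined protocol and SAP*

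**What the plan says.** The table under the instructions for dose modification or interruption during a treatment phase covers Days 2 to 57.

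- **Allergic row.** The trigger is "Allergic reaction or hypersensitivity ≥Grade 2". Drug is held for up to a week and restarted at the 400 mg level if the reaction settles to Grade 1 or less. On recurrence: "If the patient has repeat ≥ Grade 2 allergic or hypersensitivity reaction, he will be discontinued from the study medication". The sub-row directly beneath stops drug at Grade 4 or above.
- **Cardiovascular row.** The trigger is "Hypertension, Hypotension, cardiac arrhythmia ≥Grade 2", with the same hold-and-restart steps. The sub-row directly beneath stops drug at Grade 3 or above.
- **Skin rows.** Stevens-Johnson syndrome, a blistering rash of any grade, and rash or erythema multiforme of Grade 2 or more each stop drug at the first event.
- **Limit on the hold.** "The patient can be off the drug for a total 1 week before being removed from the treatment phase of the study".

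Table A sets the reduced dose at 400 mg once a day, against 400 mg twice a day at the start. The instruction for starting week 3 and open label asks, for reactions related to study treatment, only this: "Any Panax ginseng-related or identical placebo related allergic reaction/hypersensitivity that may have occurred has resolved to ≤ grade 1 severity". Section III (Discontinuation of Study Treatment) has drug stopped for an event that the investigator judges may do severe or lasting harm or that rules out continuing. C.6.2 bars open-label entry after moderate to severe toxicity in the double-blind phase.

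**The concern.** The allergic row has a gap at Grade 3. The hold begins at Grade 2 and the first-event stop is at Grade 4, so a first Grade 3 reaction is handled like a Grade 2 one: wait, then give the drug again. The row has no attribution wording, so a reaction that the investigator blames on ginseng is covered too.

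This fits poorly with judgments made elsewhere in the plan. The cardiovascular row, with the same steps, stops at Grade 3. A Grade 2 rash ends treatment at once, so in the same table it is handled more strictly than a Grade 3 hypersensitivity reaction. Exclusion criterion 1 (C.3.2.2) lists Panax allergy as a major contraindication, and Safety Monitoring in C.9 counts an attributable Grade 3 toxicity as dose-limiting.

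What is at stake is patient safety; the treatment comparison is not affected. Ginseng is given here to relieve a symptom, and the protocol says its effect on cancer-related fatigue has yet to be established. A default of re-exposure after a severe reaction attributed to it is hard to justify on that benefit.

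**Working it through.** No sample-size, power or alpha figure is involved. The check is to read the rows against each other and then test each mitigating rule.

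**Step 1: action at a first event, by grade.**

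| Grade of first event | Allergic row | Cardiovascular row |
|---|---|---|
| 2 | hold, restart at 400 mg | hold, restart at 400 mg |
| 3 | hold, restart at 400 mg | stop |
| 4 | stop | stop |

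The two rows differ only at Grade 3. This reading ties each unlabelled grade line to the row above it. Row order supports that. If the Grade 3 line were a general stop for every toxicity, the Grade 4 line below it would do nothing.

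**Step 2: attribution.** The allergic row does not mention it. The week 3 and open-label instruction, which concerns related reactions, sets a resolution grade and no ceiling on the peak grade. So nothing there takes an attributed Grade 3 reaction out of the restart path.

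**Step 3: does any other rule close the gap?**

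- *Skin rows:* they cover reactions recorded as rash, erythema multiforme, blistering or Stevens-Johnson syndrome. A reaction recorded as Grade 3 hypotension would stop under the cardiovascular row. Other Grade 3 allergic reactions are untouched.
- *One-week limit:* this removes reactions that are slow to settle. One that reaches Grade 1 within the week is restarted.
- *Section III clause:* if the investigator so judges, drug must stop. It names neither a grade nor allergy, so the table's default stands until that judgment is made.
- *Open-label bar:* a Grade 3 reaction in the double-blind phase keeps the patient out of open label, so restart then matters only up to Day 29. The table's column runs to Day 57, so a first reaction during open label falls under the same row, although Table A writes the reduced dose only to Day 29.

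The remaining case is a first Grade 3 allergic reaction with none of the skin or cardiovascular features above, settled to Grade 1 or less within a week, where the investigator has not chosen to stop.

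**Step 4: size.** Planned patients: 30 + 128 = 158. Starting on ginseng: 30 (Phase I) + 64 (Phase II) = 94. Restart dose against starting dose: 400 / 800 mg per day = one half. The documents give no rate for Grade 3 allergic reactions, so no count of re-exposed patients can be derived.

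**The case against.** The strongest reply is that the plan already contains several brakes: the skin-event stops, resolution to Grade 1 within a week, half dose, and mandatory discontinuation once the investigator judges the harm serious. Thresholds also differ by toxicity throughout the table, so a mismatch with the cardiovascular row is not in itself a contradiction. Both points stand. They narrow the affected group and make this a design choice worth improving. They do not change what the row tells a site to do by default.

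The table was also read from a PDF, and a stray fragment follows the Grade 4 line just before a page break. That stands too: the layout must be confirmed in the original before anything is amended.

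A reader might go further in three ways that the documents do not support.

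- *That sites get two conflicting instructions for a related Grade 2 event on Day 15.* The week 3 condition for other events reads "Any other Panax ginseng-related or identical placebo -related adverse event that may have occurred has resolved to ≤ grade 2 severity", while the catch-all row holds drug at Grade 2. The first is a precondition for treatment. Meeting it does not cancel a hold under the table, and the stricter rule applies.
- *That the catch-all row restarts drug after any related Grade 3 or 4 event.* The row beginning "Any Other non- hematologic toxicity assessed as Panax ginseng study drug or identical placebo - related" shows no stop line in the extracted text, but it sits right after the page break, so a line may have been lost.
- *That the dose-limiting toxicity definition or exclusion criterion 1 is breached.* The first is a trial-level stopping rule and the second an entry rule. They show what the plan regards as serious; neither says when an enrolled patient must stop.

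**Conclusion.** The point holds for the allergic row. On the table as extracted, a first Grade 3 allergic or hypersensitivity reaction, attributed to ginseng or not, is by default held for up to a week and restarted at 400 mg daily once at Grade 1 or less. Only recurrence, slow resolution, a separately listed skin or cardiovascular event, or the investigator's own decision prevents or ends that.

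The conclusion assumes that the Grade 3 and Grade 4 lines belong to the rows directly above them. The table applies to all 158 planned patients, 94 of whom start on ginseng; these are enrolment figures, not an estimate of how many would be re-exposed. The change should be made because it is cheap and protects patients. It does not call into question the efficacy analysis or the Phase I stopping rule. Whether the catch-all row lacks a stop line is an open question.

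**What to change.** First confirm in the original table which row each grade line belongs to. Then, in the allergic row, change the first-event stop from Grade 4 to Grade 3 or more, so that hold and restart applies to Grade 2 only.

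At the same time, check whether the original catch-all row has a stop line. If it has none, add one for related events of Grade 3 or more.

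Leave the Grade 2 condition in the week 3 and open-label instruction alone. It also covers hematologic events, so tightening it to Grade 1 would newly hold drug for related Grade 2 hematologic events that the table does not hold, such as neutropenia without fever.

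The cost is an amendment to the wording of one table. The downside is that a few more patients would stop study drug.
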